7.8.1 Site Effect

The consistency of the success rate over investigational sites will be assessed. Success proportions by site will be summarized. A Fisher's exact test will be used to examine the significance of a difference in the primary effectiveness endpoint using an alpha of 0.15.

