4.5 Clinical Sites & Enrollment

A minimum of three (3) and up to five (5) research sites in the United States will participate in this pivotal study. The sites will enroll a total of 120 subjects meeting all inclusion and exclusion criteria to reach a total of 110 evaluable subjects, allowing for 10 subjects lost to follow-up. It is anticipated that there will be a total of 55 evaluable subjects in each arm. Once the informed consent process is completed and final study eligibility has been confirmed, the patient will have the EndoRotor or continued ablative therapy procedure.

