7.3 Sample Size

Assuming a response rate for Barrett's esophagus with EndoRotor® ablative therapy of 80%, and for cryoablation of 50%, the study will have over 95% power to demonstrate non-inferiority (NI), given a NI delta of 10%, of EndoRotor® to cryoablation and will have 91.6% power to demonstrate superiority of EndoRotor® over continued ablative therapy using a sample size of 110 evaluable subjects, 55 in each treatment group.

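### The site check in section 7.8.1 compares success rates between sites; nothing in the plan tests whether the between-arm difference is consistent across the 3 to 5 sites

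*Combined protocol and SAP*

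**What the plan says.** Section 7.8.1 (Site Effect) is the whole plan for site consistency: "The consistency of the success rate over investigational sites will be assessed. Success proportions by site will be summarized". It then specifies that a Fisher's "exact test will be used to examine the significance of a difference in the primary effectiveness endpoint using an alpha of 0.15". It does not mention arm, the treatment difference by site, or an interaction, and it attaches no consequence to a result below 0.15.

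Related sections:
- Section 4.5: "A minimum of three (3) and up to five (5) research sites in the United States will participate".
- Section 5.2 randomizes 1:1 separately within each site.
- Section 7.1 says that tables are split by treatment arm and that percentages carry Clopper-Pearson intervals.
- Section 7.4 gives the primary logistic model: treatment, age, dysplasia grade, lesion length and disease duration. Site is not in it.
- Section 7.5 uses site as a predictor for multiple imputation. This is its only other analytic role.
- Section 7.6 states both primary hypotheses as a comparison of success proportions between arms.

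**The concern.** Whether one overall difference represents every site depends on whether that difference is similar across sites. Equal success rates across sites neither guarantee this nor are required for it.

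The protocol gives reasons to expect both kinds of site variation:
- **Prognosis may vary while the effect does not.** Section 4.12 admits residual lengths of 1 to 6 cm and either dysplasia grade, and section 5.8.3 leaves specimens to the resident pathologist.
- **The effect may vary.** Under section 5.5.3 the investigator chooses RFA or cryotherapy for control subjects, and EndoRotor speed follows user preference.

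At stake is how the multicentre result is read. A flag at 0.15 could be taken as evidence that the treatment effect is inconsistent when only case mix differs. A quiet result could be taken as reassurance about the effect when the test did not examine it.

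**Working it through.** **Inputs from the plan.** Response rates: "ablative therapy of 80%, and for cryoablation of 50"% (section 7.3). Size: "using a sample size of 110 evaluable subjects, 55 in each treatment group" (section 7.3). Sites: 3 to 5 (section 4.5). Test level: 0.15 (section 7.8.1).

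**Assumptions.** The documents give no rates by site and no split of subjects between sites. Every site-level rate below, and the equal split, is assumed.

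**The plan's own figure first.** Section 7.3 says the study "will have 91.6% power to demonstrate superiority of EndoRotor® over continued ablative therapy". With a pooled null variance and 55 per arm:

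- null SE = √(2 × 0.65 × 0.35 / 55) = 0.0910
- alternative SE = √((0.80 × 0.20 + 0.50 × 0.50) / 55) = 0.0863
- power = Φ((0.30 − 1.96 × 0.0910) / 0.0863) = Φ(1.41) = 92.1%

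This is within a point of 91.6%, so the inputs are read correctly. The plan gives no operating figure for the site test.

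**Why the two questions separate.** With 1:1 allocation within site, the pooled site rate is (EndoRotor rate + control rate) / 2.

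| Scenario, 3 sites | EndoRotor % | Control % | Difference, points | Pooled site rate % |
|---|---|---|---|---|
| Prognosis differs only | 65 / 80 / 95 | 35 / 50 / 65 | +30 / +30 / +30 | 50 / 65 / 80 |
| One site reversed | 90 / 80 / 50 | 40 / 50 / 80 | +50 / +30 / −30 | 65 / 65 / 65 |

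In the first row the difference is constant and the pooled rates span 30 points. In the second, the difference changes sign and the pooled rates are equal.

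**Methods compared by simulation.**
- Site test: Fisher-Freeman-Halton on the site-by-outcome table, table probability ∏C(nᵢ, xᵢ) / C(N, t). A chi-square stand-in gave similar results.
- Homogeneity: Cochran's Q = Σwᵢ(θᵢ − θ̄)², with wᵢ the inverse variance and K − 1 degrees of freedom, where θᵢ is the site's log odds ratio or risk difference.
- Also a likelihood-ratio test of the treatment-by-site interaction in logistic regression.

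**Results with 18 per arm per site, proportion flagged at 0.15.** The by-arm column applies the site test within each arm at 0.15 and counts a flag in either.

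| Scenario | Site test, arms pooled | Site test, by arm | Homogeneity test (Q) |
|---|---|---|---|
| Prognosis differs only | 83–86% | 85% | 12% (log odds ratio), 14% (risk difference) |
| One site reversed | 9–12% | 97–98% | 98% |

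**Further scenarios, 55 per arm, equal sites.**

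| Scenario | Site test, arms pooled | Likelihood-ratio interaction |
|---|---|---|
| 80% v 50% at every site, 3 sites | 12% | 18% |
| 80% v 50% at every site, 5 sites | 10% | 22% |
| Constant odds ratio 4, control 40/50/60% | 43% | 18% |
| Constant odds ratio 4, control 30/50/70% | 92% | 19% |
| Differences +45/+30/+15, pooled 65% at each site | 12% | 47% |
| Control 50% everywhere, EndoRotor 95/80/65% | 34% | 67% |

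The first two rows show that the Fisher test keeps its level for the question it literally asks, and that the asymptotic interaction test exceeds its level. The likelihood-ratio figures therefore overstate the gain somewhat. With Cochran's Q, where site effects do not cancel, the contrast was 37% for the pooled site test against 39–42% for homogeneity.

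**Sparse cells and scale.** In the constant +30-point scenario, the chance that all 18 EndoRotor subjects succeed at the 95% site is 0.95¹⁸ = 0.40. An ordinary logistic interaction then meets separation. With 5 sites, 11 per arm and 80%, the chance of at least one all-success EndoRotor cell is 1 − (1 − 0.80¹¹)⁵ = 0.36. The odds ratios in the same +30-point scenario are (0.65/0.35)/(0.35/0.65) = 3.4, (0.80/0.20)/1 = 4.0 and (0.95/0.05)/(0.65/0.35) = 10.2. A constant risk difference is therefore not a constant odds ratio, and with 55 per arm the likelihood-ratio test flags that scenario 33% of the time.

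**The case against.** The strongest defence is that section 7.8.1 does what it announces: it looks at success rates by site, with a valid test, as a supportive summary that no decision depends on. It lies outside the testing sequence of section 7.8.3. That stands, and it limits the point to an improvement.

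A reader might go further and infer that the test pools the arms, that a reversed site would go unseen, and so that the check gives wrong answers in both directions. The documents do not support this:
- Section 7.8.1 never says the arms are pooled. Section 7.1 splits tables by arm, so the by-site proportions can be read as arm-specific with intervals, and a reversal would be visible there.
- A Fisher test by site within each arm would flag the reversed scenario 97–98% of the time. The missed reversal belongs to the pooled reading only, and there it needs site effects that nearly cancel.
- Nothing in the documents makes the assumed site rates likely.

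What survives on every reading is narrower. Fisher tests of site with arms pooled, of site within each arm, or of treatment within each site are none of them tests of homogeneity of the treatment effect. The tendency to flag pure prognostic differences holds for both by-site readings, pooled and by arm.

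It is also fair to object that a replacement has weaknesses: low power, sparse cells, and dependence on the effect scale. These bear on which homogeneity test to choose.

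**Conclusion.** The point holds as a cheap improvement. The plan tests whether success varies by site and does not test whether the between-arm difference does. Used as evidence about the latter, the planned test can mislead. It flags about 85% of trials with a constant +30-point effect and control rates of 35/50/65%, pooled or by arm, against 12–14% for homogeneity tests. If the arms are pooled, it flags about 10% when one site is reversed and pooled rates are equal, against 98%.

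These sizes rest on assumed site rates and equal sites. A milder prognostic spread (control 40/50/60%, odds ratio 4) brings the unwanted flags down to 43%. When site effects do not cancel, the advantage of a homogeneity test in detection can be small (37% against 39–42%).

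The primary test, its alpha, the 10% margin and the sample size are unaffected.

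**What to change.** Reword section 7.8.1 before the data are unmasked:

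1. Replace the Fisher test with a test of homogeneity of the treatment effect across sites at 0.15, by a method that copes with sparse cells. Options are an exact homogeneity test, a penalized logistic interaction, or a homogeneity test on the risk-difference scale of the primary comparison. Name the method and the scale.
2. Report, for each site, the success rate in each arm and the treatment difference with its confidence interval.
3. Keep the by-site success proportions as description.

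The cost is a few lines of text and code, with no new data. The downsides should be stated in the plan. Power is modest for moderate heterogeneity (47% for +45/+30/+15, even with the likelihood-ratio version), so a quiet result is not proof of consistency and the site-specific intervals matter more than the p-value. Asymptotic likelihood-ratio versions run above nominal (0.18 to 0.22 at 0.15), which favours an exact or penalized method.

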7.8.2 Interim Analysis

No interim analysis of effectiveness endpoints will be performed.

7.8.3 Multiplicity

In the event that the primary effectiveness test of non-inferiority fails to reach significance, further endpoint testing will cease. If the test of non-inferiority is successful, then testing for superiority will proceed. If superiority is demonstrated for the primary effectiveness endpoint, then the secondary endpoint will be tested.

7.8.4 Additional Summaries

Subject baseline and demographic characteristics, including medical history, and operative characteristics and outcomes will be summarized for each treatment arm. Subject disposition and protocol deviations will be summarized by count and percentage. All summarized data will be supported by subject line listings.

8.0 INVESTIGATOR RESPONSIBILITIES

The Site Investigators are responsible for signing the Investigator agreement prior to the commencement of the study and for ensuring that this trial is conducted according to this clinical protocol, Good Clinical Practice (GCP) Guidelines, the Declaration of Helsinki, US FDA requirements and any other local, or IRB requirements that apply to Clinical Investigations at their center.

It is also the Investigator's responsibility to ensure that all sub-investigators and staff assisting with this study have the appropriate qualifications and that they complete training on the investigational devices and study procedures and that patient confidentiality is respected.

8.1 Institutional Review Board (IRB) Approval

The Investigator at each site is responsible for securing IRB approval for this study protocol and the Informed Consent documents prior to any patient enrollment. The local IRB for each specific institution or for multiple institutions must review and approve this study protocol and the specific Informed Consent forms to be used at that site **prior** to enrollment of the first patient. The Sponsor **must** also review and approve the final Informed Consent documents prior to their use. The Sponsor and/or their designated CRO must receive a copy of any IRB correspondence, as well as the final approval letter and the final approved Informed Consent from each IRB. Investigators are also responsible for submitting and obtaining a continuing review (at intervals

not greater than once a year) of the study by their IRB.

The Investigator or clinical site staff will not make amendments to this protocol or the Informed Consent forms without **PRIOR** written approval from the Sponsor. All approved amendments must then be submitted to the local IRB and the FDA, as appropriate for approval.

8.1.1 Withdrawal of Approval

If the Investigator's IRB withdraws their approval to conduct this study for any reason, the Investigator **must** notify the Sponsor and their designated CRO as soon as possible, but in no event later than **five working days** after the withdrawal of the approval.

8.2 Informed Consent

The Investigator is responsible for ensuring that all local, national, GCP, Declaration of Helsinki, and US FDA guidelines and regulations are met when completing the informed consent process. Written, informed consent is to be obtained whenever possible for each patient **prior** to treatment. Additional details regarding the informed consent process are also available in the Section 4.8 Screening and Enrollment of this protocol.

8.3 Clinical Data Collection

Two-ply, paper Case Report Forms (CRFs) will be used to collect complete and accurate records of the clinical data from this study according to the Good Clinical Practices (GCP) requirements. The Investigator and/or study staff under his/her direction is responsible for accurately recording the clinical data for this study and entering the data into the CRF and upload to the Sponsor's secure web server in a timely manner. The required form / report and timeframes are provided in **Table 1** below:

Table 1. Form/Report and Required Submission Timeframe

| Form/Report | Required Submission Timeframe |
|-----------------------------------|---|
| Enrollment/Treatment Notification | Enter onto CRF and upload to Sponsor's secure web server within 48 hours . |
| Baseline and Treatment CRFs | Enter onto CRF and upload to Sponsor's secure web server within 7 days of the index procedure. |
| Discharge Data | Enter onto CRF and upload to Sponsor's secure web server within 7 days of discharge . |
| Follow-up Forms | Enter onto CRF and upload to Sponsor's secure web server within 7 days of follow-up visit. |
| Serious Adverse Events | Notify Sponsor via email within 24 hours of knowledge. Enter onto CRF and upload to Sponsor's secure web server within 48 hours of knowledge. |
| Adverse Events | Enter onto CRF and upload to Sponsor's secure web server within 7 days of knowledge. |
| Device malfunction / Failure | Notify Sponsor via email within 48 hours of knowledge. Enter onto CRF and upload to Sponsor's secure web server within 48 hours of knowledge. |

| | |
|-------------------------|---|
| Deviations from the CIP | Enter onto CRF and upload to Sponsor's secure web server within 7 days of knowledge. |
|-------------------------|---|

8.4 Device Accountability

The Sponsor will ship investigational devices only to the designated Investigators participating in this study following internal requirements, FDA IDE Conditional Approval and IRB approval. All Investigators will be responsible for providing a secure storage location for the investigational devices, supervising investigational device use, and the disposal and/or return of the investigational devices as instructed by the Sponsor. In addition, all Investigators will maintain records to document the receipt, use and disposition of all investigational devices received by their site. The Sponsor, designated monitor and/or CRO will also maintain records of all shipments and disposition of the investigational devices. The Sponsor and/or their authorized CRO will routinely inspect the clinical site inventory records for device accountability at the clinical sites participating in this trial.

8.5 Clinical Site Records

Records to be maintained by the Investigator and research staff include:

- Clinical trial investigational plan and all amendments
- Signed clinical trial agreement
- Investigator agreements
- IRB approval letter, including informed consent documents
- IRB membership list
- Correspondence relating to the trial
- CVs for all investigators and key personnel
- Clinical monitor sign-in log
- Patient screening / enrollment log
- Lab certification and lab test normal ranges
- Reports (includes annual reports, final reports from investigator and sponsor)

The following records must be maintained for each patient enrolled in the trial:

- Signed Patient Informed Consent Form
- All completed CRFs
- Supporting documentation of any complications and Serious Adverse Events

Interscope recommends that the investigator retain copies of procedure reports, procedure notes and the results of any interventional procedures that occur after the endoscopy procedures.

8.6 Investigator Reports

8.6.1 Serious Adverse Events (SAEs) & Unanticipated Adverse Events (UAEs)

The Investigators will report by telephone, email or fax any SAEs or UAEs as soon as possible, (within 24 hours) of the Investigator becoming aware of the event, to the Sponsor and the CRO. Additionally, SAEs and UAEs should be reported to the IRB and/or FDA (if applicable) per the clinical site guidelines. The Serious Adverse Event form is to be uploaded to the Sponsor's secure web server within 48 hours of the event. The contact information for reporting SAEs and UAEs is provided in the Study Contact section of this protocol.

8.6.2 Device Malfunctions

The Investigators will report any Device Malfunction that occurs to Interscope as soon as possible, or within 48 hours of the Investigator becoming aware of the event. The report may be made by telephone, email or fax. Additionally, when a device malfunction occurs, or is suspected to occur during treatment, the Investigator must keep the device in a safe storage facility until an investigation can be completed and/or the designated monitor or a Sponsor representative directs the Investigator or study staff to return the device to Interscope for investigation.

8.6.3 Deviations from the Investigational Plan

The Investigator must notify Interscope and/or the CRO of any deviation from the Investigational Plan. The Investigator should also notify the IRB and/or FDA as required per their local requirements. This notice must occur as soon as possible, but in no case longer than five working days after the Investigator becomes aware of a serious deviation. Serious deviations include those that involve the informed consent process, the inclusion/exclusion criteria of the study or any deviation that involves or leads to a serious adverse event in a study participant.

8.7 Clinical Site Reports

Investigators are required to prepare and submit to Interscope complete, accurate and timely reports on this investigation when necessary according to **Table 2** below:

Table 2. Responsibilities for Preparing and Submitting Reports

| Type of Report | Prepared by Investigator for | Time of Notification |
|--|------------------------------|--|
| Enrollment/Treatment Notification | Interscope | Within 48 hours. Automatic email notification is sent to Interscope. |
| Serious adverse events | Interscope, IRB | Within 24 hours of knowledge of event |
| Unanticipated complications | Interscope, IRB | If serious or life threatening within 24 hours of knowledge of event |
| Patient withdrawal | Interscope | Within 10 working days |
| Withdrawal of IRB approval | Interscope | Within 5 working days |
| Annual progress report | Interscope, IRB | Submitted annually |
| Protocol Deviations | Interscope, IRB | Within 5 working days |
| Informed consent not obtained from patient | Interscope, IRB | Within 5 working days |

| | | |
|---|-----------------|-----------------|
| Final report | Interscope, IRB | Within 3 months |
| Other information upon the request of the IRB, FDA, or Interscope | As appropriate | As requested |

8.8 Investigator's Final Report

Upon completion or termination of the Interscope Study the principal investigator must submit a final written report to Interscope and the IRB as required by the IDE regulations. The report must be submitted within 3 months of completion or termination of the trial. The investigator's final report will include:

- Introduction. A brief description of the rationale and objectives of the trial.
- Methods. A description of the methods employed and any deviations from the investigational plan.
- Trial Population. A statement of the number of subjects evaluated; of the number of dropouts and reasons for them; and description of the initial nature and severity of medical conditions for which the subjects were evaluated.
- Results and Discussions. A clinical assessment of the effect of the investigational treatment on the medical condition of the subjects and a description of complications reported with an indication of their relationship to the investigational treatment.
- Conclusion. A summary statement of the principal investigator's opinion of the effectiveness of the investigational treatment in the subjects enrolled at his/her investigational site.

8.9 Deviations from Protocol

The investigator will not deviate from the protocol without the prior written approval of Interscope except in medical emergencies or in unforeseen, isolated instances where minor changes are made that will not increase the patient's risk or affect the validity of the trial. In medical emergencies, prior approval for protocol deviations will not be required; however, Interscope's CRO must be notified within 5 days of the incident.

8.10 Site Record Retention Policy

Records and reports will remain on file for a minimum of two (2) years after the latter of either the completion/termination of the investigational trial or the date the investigational device receives FDA clearance. They may be discarded upon notification by Interscope. To avoid error, the principal investigator should contact Interscope before the destruction of any records and reports pertaining to the trial to ensure they no longer need to be retained.

In addition, Interscope should be contacted if the principal investigator plans to leave the investigational site so that arrangements can be made for transfer of records and the remaining follow-up (if any) in the study.

8.11 Investigator Access to the Data and Publication Policies

At the conclusion of the trial, a multicenter publication/presentation reporting the primary results will be prepared and presented at a major medical meeting. A multicenter publication will also be prepared for publication in a reputable scientific journal. The publication of results from any single center experience within the trial is strongly discouraged until the multicenter results have been prepared, presented and submitted for publication (normally 1 year following the completion of the study). The analysis of other pre-specified

and non-pre-specified endpoints will be performed by Interscope. For purposes of timely abstract presentation and publication, such secondary publications will be delegated to the appropriate principal authors, and final analyses and manuscript review for all multicenter data will require the approval of the Interscope. The ENDOROTOR study will be registered with Clinicaltrials.gov per applicable requirements.

